In Teri et al. ⁽³⁰⁾ the differences in RMBPC reactivity scores ⁽²⁾ between baseline and post-intervention visit were -1.6(SD=7.6) with an effect size of 0.21 in care partners in the control group (routine medical care), and -5.8(SD=9.8) with an effect size of 0.59 in care partners in the intervention group (the ABC group). The effect size of difference in change in RMBPC ⁽²⁾ reactivity score between the two groups was 0.38. Based on this study, we conservatively determined the sample size calculation with an effect size of difference in pre-post intervention change as 0.3. To achieve at least 80% power to detect such a difference in a study design with three repeated measurements and an Intra-Class Correlation (ICC) =0.5 to 0.6 in compound symmetry covariance structure, we need at least 117 to 128 subjects/each group, for alpha = 0.05.

We anticipate an increase in power due to our conservative approach, e.g., based on three time repeated measures instead of 6 time points (Figure 2) and smaller effect size between intervention

and control groups on the RMBPC (compared to 0.59 Teri et al.)⁽³⁰⁾. We will use this increase in power to compensate for the complexity of the proposed model when adjusting covariates are taken into consideration. For self-efficacy, based on estimates from the STELLA-FTD pilot, group sample sizes of 128 will achieve 80% power to detect a difference of 0.32 at alpha level of 0.05, which is reasonable given pilot data trends⁽⁴²⁾.

In determining the sample size, we took attrition into account. Based on our experience⁽²⁹⁾, it is likely that up to 15% of the sample will withdraw due to schedule demands, illness and death, thus we will over-recruit to enroll 300 care partners.

5) Study Population

a) Number of Subjects

Participants. Informed by our power analysis, we will enroll a total sample of 600 participants: 300 family care partners and their 300 care recipients with FTD. For our study “family care partner” includes any person who is considered “family” to the person with FTD, such as direct relations, fictive kin, close friends and neighbors. “Care recipient” is defined as an individual with an FTD diagnosis: bv-FTD, PPA, progressive supranuclear palsy (PSP), corticobasal degeneration (CBD), or FTD with motor neuron disease⁽⁴³⁾.

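### The 117 to 128 per group matches a time-averaged difference, but H1 tests group × time, so the claim of at least 80% power is not shown for the primary test

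*Combined protocol and SAP*

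**What the plan says.** Section 4, sample size calculation/power analysis, starts from a cited dementia trial. Changes in RMBPC reactivity there "were -1.6(SD=7.6) with an effect size of 0.21 in care partners in the control group" "and -5.8(SD=9.8) with an effect size of 0.59 in care partners in the intervention group", and the effect size for the difference in change in "reactivity score between the two groups was 0.38". The plan then states that "we conservatively determined the sample size calculation with an effect size of difference in pre-post intervention change as 0.3". For at least 80% power with three repeated measurements and ICC 0.5 to 0.6 under compound symmetry, it concludes that "we need at least 117 to 128 subjects/each group, for alpha = 0.05". No formula or tested contrast is named.

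The section expects extra power from two sources: the calculation is "based on three time repeated measures instead of 6 time points", and it assumes a smaller effect between intervention "and control groups on the RMBPC (compared to 0.59" in the cited trial). It assigns that extra power to covariate adjustment and model complexity. On attrition it says "it is likely that up to 15% of the sample will withdraw due to schedule demands, illness and death", and enrols 300 care partners.

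Section 8, Aim 1, H1 specifies a mixed model with group, time as a continuous variable, their interaction and random intercepts. The primary test is the two-sided 0.05 test of the interaction coefficient over the intervention period. Weeks 20 and 36 are handled in similar, separate analyses.

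**The concern.** A time-averaged difference and a group × time slope are different contrasts with different variances. A higher within-subject correlation makes a time average less precise and a slope more precise. The plan's required size goes up with the ICC (117 at 0.5, 128 at 0.6), which is how a time average behaves. It also describes 0.3 as a difference in pre-post change, which a mean over pre and post visits does not measure.

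If the power statement belongs to another contrast, readers do not know what effect the primary test can detect, and a null result cannot be set against a known detectable difference. The plan also spends a power surplus that it has not calculated.

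**Working it through.** **Inputs.** From section 4: d = 0.3, m = 3 measurements, ICC ρ = 0.5 or 0.6, compound symmetry, 80% power, alpha 0.05. From H1: two-sided test, continuous time, random intercept. Evaluable number: 300 × 0.85 / 2 = 127.5, taken as 128 per group (1:1 allocation assumed; the ratio is not stated). Partial data are retained (section 6, Measures), so the information lies between 128 and 150 per group.

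**Step 1: reproduce the plan's figure.** (1.960 + 0.842)² = 7.849. For a time-averaged difference, n = 2 × 7.849 × [1 + (m − 1)ρ] / (m d²):

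- ρ = 0.5: 2 × 7.849 × 2.0 / 0.27 = 116.3, so 117.
- ρ = 0.6: 2 × 7.849 × 2.2 / 0.27 = 127.9, so 128.

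Both ends match. Seven alternatives were tried (one-sided versions, slope or change, and ANCOVA or change scores with one or two pre or post visits). None gives this pair.

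**Step 2: power for the H1 coefficient.** Let tc be the centred visit weeks, f the fraction of the effect present at each visit, A = Σ(tc·f) and Sxx = Σtc². Under compound symmetry the slope difference is b = d·s·A/Sxx with variance 2(1 − ρ)/(n·Sxx). Here s = √(2(1 − ρ)) if 0.3 is in SD-of-change units and s = 1 if it is in outcome-SD units.

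In SD-of-change units ρ cancels and b/SE = d·A·√(n/Sxx). For weeks 4, 8 and 12, A = 4 and Sxx = 32, so b/SE = 0.3 × 4 × √(128/32) = 2.40. Power is Φ(2.40 − 1.96) = 67%, and the size needed is 7.849 × 32 / (0.09 × 16) = 174.4, so 175. Centred time at week 8 is zero, so the effect at that visit does not matter.

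In outcome-SD units, b/SE is divided by √(2(1 − ρ)). At ρ = 0.5 this is 1, so the two units coincide. At ρ = 0.6 it is √0.8.

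| Visits (weeks) and effect shape | A; Sxx | Power at 128, SD-of-change | n per group for 80% | Effect with 80% power at 128 | Power at 128, outcome SD, ICC 0.6 |
|---|---|---|---|---|---|
| 4, 8, 12 | 4; 32 | 67% | 175 | 0.35 | 77% |
| 1, 4, 12 | 6.33; 64.67 | 76% | 141 | 0.31 | 85% |
| 1, 4, 8, 12, linear from week 4 | 6.625; 68.75 | 77% | 137 | 0.31 | 86% |
| 1, 4, 8, 12, effect only at post | 5.75; 68.75 | 65% | 182 | 0.36 | 75% |
| 1, 4, 8, 12, complete by week 8 | 7.5; 68.75 | 87% | 107 | 0.27 | 93% |

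Simulation of the random-intercept model (20,000 runs, 128 per group, SD-of-change units) gave 68%, 76%, 77%, 65% and 87% in the same order. At 150 per group, the first three rows rise to 74%, 82% and 84% in SD-of-change units.

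**Timing.** Week 12 for Post Assessment 1 is inferred: Post-Assessment 2 is two months after the end and H1 places it at week 20. Using week 13 changes the 67% and the 77% (linear) by less than one point.

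**Step 3: the source effects.** 1.6/7.6 = 0.21 and 5.8/9.8 = 0.59, so 0.59 is the change within the intervention arm. 0.59 − 0.21 = 0.38 subtracts two effects standardised by different SDs. On a pooled SD of change, √((7.6² + 9.8²)/2) = 8.77, and 4.2/8.77 = 0.48 (equal arms assumed). Using 9.8 gives 0.43, and using 7.6 gives 0.55.

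**The case against.** No formula is named, and an average of several post-baseline change scores, with the ICC defined among those changes, would also give 117 and 128. That is true, and it fits the description of 0.3 better, but the text does not say it and it is still not the H1 test.

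The size of any shortfall is not fixed. The readings above run from 65% to 93% at 128 per group, and the formula that yields 117 and 128 is naturally in outcome-SD units, which are the more favourable ones at ICC 0.6. This stands, and it limits the conclusion to power not being shown.

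Planning at 0.3 leaves a margin. At 0.38 in SD-of-change units, weeks 4, 8 and 12 give b/SE = 0.38 × 4 × 2 = 3.04 and 86% power. This also stands, but 0.3 is the stated planning value.

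Using all six visits could supply the claimed reserve. With the effect built up over weeks 4 to 12 and held to week 36, power at 128 is 83% in SD-of-change units, and 90% in outcome-SD units at ICC 0.6. If the effect instead fades linearly to zero by week 36, the linear interaction has almost no power. H1 is in any case confined to the intervention period.

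Table 2 implies a mid-intervention visit nearer week 9 than the week 8 shown in Table 3. At weeks 4, 9 and 13, power at 128 in SD-of-change units is 63.5% if the effect appears only at post and 70% if it is complete by mid-intervention, so the 67% then depends modestly on shape. Figure 2, the design schematic, is not in the text reviewed and may show which three visits were meant. It could not make a time-averaged calculation apply to a slope test.

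**Conclusion.** The concern holds. The stated 80% power is for a contrast that H1 does not test, whichever visits, SD unit or effect shape are assumed. For the tested coefficient at 0.3 and 128 per group, three visits at weeks 4, 8 and 12 give 67% in SD-of-change units, the scale of the within-arm effects quoted in section 4. Outcome-SD units at ICC 0.6 give 77%. Adding week 1 raises these to 77% and 86% with linear accrual from week 4. Some readings exceed 80%, so this does not establish that the trial is too small.

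The claimed reserve is not quantified, and its 0.59 comparator is not a between-group effect. The figures rest on compound symmetry, 1:1 allocation and the inferred week 12. The validity of the H1 test and its estimate is not affected.

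**What to change.** Keep N. Replace the power sentence in section 4 with one calculated for the H1 group × time coefficient at 128 per group. It should state the visits used, the SD that standardises 0.3, the assumed effect shape, the power, and the effect detectable with 80% power. Name the same visits in H1. If SD-of-change is the intended unit, the wording could be as follows, keeping only the alternative that matches the H1 visits:

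> With 128 evaluable care partners per group, two-sided alpha 0.05, compound symmetry and a 0.3 SD-of-change difference at post-intervention, power for group × time is about 67% using weeks 4, 8 and 12 (80% power at 0.35), or about 77% using weeks 1, 4, 8 and 12 with linear accrual from week 4 (80% power at 0.31).

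If outcome-SD is intended, state the ICC and use the corresponding figures. Remove the comparison with 0.59, or replace it with a between-group effect on one stated SD. Quantify the gain from six time points under a stated effect shape, or delete it.

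The cost is one recalculation and some wording. Enrolment, visits and procedures do not change, though the stated power may be less favourable.

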If the potential participant meets the pre-screening criteria, the study RA will meet with them via phone or video for a more detailed screen. This screen provides enough information to ascertain if the potential participant is eligible. The screening process will not adversely affect the rights and welfare of the potential subjects. Following OHSU screening protocol, we will seek their verbal permission to screen them. Prior to other questions, we will review their right to privacy and OHSU phone numbers will be provided. If they are not eligible, the pre-screen form and all data will be deleted. Please see HIPAA Waiver request.

If the potential participant is eligible, they will be automatically connected to the eConsent. Screening data may be stored on Excel files on the OHSU OneDrive, the H or X drives and/or the Qualtrics and REDCap databases.

f) Consent Process

Eligible participants will be directed to an online eConsent. The eConsent describes the study in detail. The eConsent provides details about the study and has questions to confirm understanding. If the participant's answers indicate poor understanding of the eConsent, the RA will contact them to review. Upon completing the eConsent, participants will provide their initials to attest they have reviewed the consent. The participant will retain a copy of the eConsent; the STELLA-FTD study will not retain copies of the eConsents. The eConsent can be accessed on a computer, smartphone, or other device. At the first STELLA-FTD session, the PI will review the key points of the consent with the participants.

Participants will be advised that the study team is obliged to report any elder abuse. Participation in this research is not meant in any way to replace regular care.

We will also collect an eConsent for person with FTD because we will collect data about them and if they enter the recorded sessions, their privacy may be compromised. If the person with FTD is not capable comprehending eConsent we will seek consent from their legally authorized representative ^(49, 50). If the person with FTD is capable of consenting and does not consent, their care partner cannot participate in STELLA-FTD. Consent forms will contain information about data sharing and management, per NIH policy. ⁽⁵¹⁾ All consent processes will be approved and monitored by OHSU IRB.

Due to the complicated nature of FTD conditions, the potential subjects' decisional impairment may be intermittent, progressive, or complete.

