Once a care partner is deemed eligible for the study, and prior to the care recipient's consent, we will ask the family care partner these questions (either on a videoconference call or survey).

Do you think your family member would be able to provide consent for this study? The person with dementia would need to do the following:

- i. Talk with the STELLA-FTD staff on the phone for about 30 minutes to review the consent form
- ii. Understand the risks and benefits
- iii. Make an informed decision about whether or not he or she would like to consent

If the family care partner does not think the person with FTD can meet these criteria, we will ask the family member to have the LAR review the consent form and consent on behalf of the person with FTD.

We ask the care partners if they are the legal authorized representative. If yes, the team will document this and proceed with send them the eConsent for the care recipient.

If the care partner is not sure they are the LAR, the RA will read this list to see if they meet the criteria:

- 1) Health care representative who is legally authorized by a valid advance directive or health care power of attorney
- 2) Court-appointed guardian
- 3) If the above two do not exist or cannot be located with reasonable effort, another surrogate who knows and can represent the previously expressed wishes of the potential subject, in the following order of preference:
 - a) Spouse or registered domestic partner
 - b) Adult child
 - c) Either parent
 - d) Adult sibling
 - e) Adult designated by others on this list, if no one on the list objects
 - f) Other adult relative or friend who has an established relationship with the potential subject.

If the LAR is not the care partner, ask the care partner to please contact the LAR to arrange for them to be present during the consent appointment.

If the person with FTD is not able to consent, their eConsent will be emailed to the care partner. The care partner will be advised to review with the care recipient if possible. The care partner will sign for the person with FTD.

FTD is a progressive disease. Participants will not regain the capacity to consent as the study progresses.

The person with FTD will not have any role in the study. We will only collect information about them. Because there is a risk of loss of confidentiality if they enter the room during the video sessions, we are seeking their consent.

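### When the care partner is not the legally authorized representative, the consent section names two different signatories for a person with FTD who cannot consent

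*Combined protocol and SAP*

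**What the plan says.** All the signatory rules are in section 5) Study Population, f) Consent Process.

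- **General rule.** "If the person with FTD is not capable comprehending eConsent we will seek consent from their legally authorized representative".
- **Operational step.** When the care partner thinks the recipient cannot consent, the plan says "we will ask the family member to have the LAR review the consent form and consent on behalf of the person with FTD".
- **Establishing who the LAR is.** The care partner is asked whether they are the LAR. If so, this is documented and the recipient's form is sent to them. If they are unsure, the research assistant reads out a ranked list: health care representative, court-appointed guardian, then other surrogates in order of preference, ending with another adult relative or friend.
- **LAR is someone else.** "If the LAR is not the care partner, ask the care partner to please contact the LAR to arrange for them to be present" at the consent appointment.
- **Next paragraph.** If the recipient is unable to consent, the form is emailed to the care partner, who is advised to go through it with the recipient if possible. Then: "The care partner will sign for the person with FTD".

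Section 5 a) defines family care partners broadly, "such as direct relations, fictive kin, close friends and neighbors". Section 5 c) expects recipients to be decisionally impaired in most cases.

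On the course of capacity, the consent section says that "decisional impairment may be intermittent, progressive, or complete" and later that "Participants will not regain the capacity to consent as the study progresses". The section closes by pointing to a Decisionally Impaired Adults Supplement for details.

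**The concern.** The last signature instruction drops the condition on which the rest of the section rests. Everything before it makes LAR status the test of who may consent for a person without capacity. This paragraph makes incapacity alone the trigger and gives the signature to the care partner.

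Staff who treat it as the operative instruction would send the form to the care partner whether or not that person is the LAR. At stake is whether a decisionally impaired participant is enrolled on the signature of someone entitled to give it. That protects participants' rights and cannot be repaired by analysis afterwards.

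**Working it through.** No formula applies and the plan gives no figure to reproduce. The check sets the instructions side by side, in the order of the consent section.

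| Step | Trigger | Who consents or signs |
|---|---|---|
| 1. General rule | Recipient cannot comprehend the form | LAR |
| 2. Operational step | Care partner thinks recipient cannot consent | LAR |
| 3. Care partner is the LAR | LAR status documented | Care partner, as LAR |
| 4. Care partner unsure | Ranked list read out | Whoever the list identifies |
| 5. LAR is someone else | Care partner is not the LAR | LAR, asked to attend |
| 6. Next paragraph | Recipient not able to consent | Care partner, no LAR condition |

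**Case A: the care partner is the LAR.** Steps 1, 2, 3 and 6 all lead to the same person. There is no conflict.

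**Case B: the care partner is not the LAR.** Steps 1, 2 and 5 lead to the LAR. Step 6 leads to the care partner. The two cannot both be followed.

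**Can step 6 be confined to case A?** The text does not say so, and two features count against it. Step 3 already tells staff to send the form to a care partner who is the LAR, so step 6 would largely repeat it. Step 6 also directly follows step 5, the branch in which the LAR is another person.

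**Can case B arise?** Yes. Step 5 provides for it. Friends and neighbors may be care partners, and a friend comes last in the order of preference, so qualifies only if nobody ranks higher. Nor is it limited to friends: an adult child ranks below a spouse or registered domestic partner.

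**How many recipients?** The number signed for by someone other than the LAR would be

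300 × (share lacking capacity) × (share of those whose care partner is not the LAR) × (share of those in which step 6 is followed instead of step 5).

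Only the 300 is in the documents. Section 5 c) says impairment is likely but gives no percentage, and the other two shares are not addressed. The number cannot be estimated.

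**Secondary check.** Impairment that may be intermittent implies periods in which a person can consent. The statement that participants will not regain capacity denies this. The two sentences do not fit together as written.

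**The case against.** The strongest defence is that the section states the LAR rule more than once, documents LAR status before sending the form to a care partner, supplies a ranked list and has a separate branch for an LAR who is someone else. On that view one loosely worded sentence does not displace the rest. The list is also broad enough that many care partners will qualify. The supplement may settle the point, and the section places all consent processes under IRB approval and monitoring.

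This stands as a limit on the consequence. It does not remove the conflict: the sentence is unqualified, it is the last signature instruction given, and if the supplement states the LAR rule, this sentence contradicts it.

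A reader might also infer stronger things that the documents do not support:

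- **That recipients will be enrolled without valid consent.** This happens only if the last paragraph is followed when the care partner is not the LAR. The text supports could, not would.
- **That invalid consents would remove pairs from the analysis and use up the allowance for loss** (300 − 2 × 128 = 44). Nothing says a defective recipient consent removes the care partner's data. The primary outcome is reported by the care partner, who consents separately, and recipients take no part in the intervention.
- **That a care partner could declare incapacity in order to join.** The plan does say "If the person with FTD is capable of consenting and does not consent, their care partner cannot participate in STELLA-FTD", and it asks the care partner's opinion of capacity first. To read a motive into that is speculation, and the care partner is also advised to review the form with the recipient where possible.

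**Conclusion.** The contradiction is in the current text and is certain as a matter of wording: when the care partner is not the LAR, the consent section names two signatories. The consequence is conditional. A recipient could be enrolled on the signature of someone without authority if the last paragraph is taken literally.

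The size is unknown, and no effect on sample size, power or analysis is shown. The conclusion rests on the consent section as supplied; actual practice cannot be judged without the supplement. Even so, a rule that can name the wrong signatory for decisionally impaired participants should be corrected, whatever the number affected. The mismatch over intermittent impairment is real but secondary.

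**What to change.** Reword the paragraph along these lines:

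*If the person with FTD is not able to consent, the eConsent is sent to the LAR identified from the list above, and only the LAR signs. The care partner signs only when documented as the LAR.*

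The advice to review the form with the recipient where possible can stay. Check the supplement and the eConsent routing against the new wording so that one signatory rule applies throughout.

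Secondary change: reconcile the sentence on intermittent impairment with the one saying capacity will not return.

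The cost is protocol wording, eConsent routing and a short delay for pairs whose LAR is someone else. The contradiction can be resolved without a staff assessment of capacity for recipients judged unable to consent; that would be a new procedure, not a correction of wording.

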Delivery monitoring. All STELLA-FTD sessions will be recorded and recordings will be stored on a secure server that the fidelity assessment team can access via the OHSU secure filesharing system. The team will view a randomly-identified subsample (15%) of the recordings to evaluate procedural, documentation and theoretical fidelity. Fidelity items are scored using a binary rating of "1" (present) or "0" (absent), with clearly defined characteristics required for either rating. Inter-rater agreement on video assessments will be measured (62).

Standardized checklists and criteria will be used for each fidelity domain. Guides will be required to complete session content checklists to ensure essential study components are addressed. Session duration will be monitored to prevent potential threats of variance in dosing between trial groups.

We will actively monitor for potential contamination between the test and control groups. Our study design, operationalized procedures and ongoing and diligent fidelity monitoring will aid in early identification and management of fidelity concerns (60).

Taken together, the STELLA-FTD intervention will be implemented within an adequately-powered research design that will test the proposed hypotheses. We will have a fidelity assessment process in place to ensure adherence to protocol. Our intervention will allow us to conduct the trial efficiently and provide interpretable results. To answer our research questions, we will employ relevant measures.

Anticipated challenges. Scheduling Care Partners may be difficult. Thus, the protocol allows the following concessions:

- The study team may alter the session schedules due to holidays, illness or other scheduling issues.
- There may be two sessions may be doubled in a week if scheduling challenges.
- Care Partners can skip up to 3 sessions and still remain in the study.
- If there are more Care Partners than available Guides, the Care Partners may have to wait to the sessions. We will enroll them and have them do the weekly survey until there is space. Four weeks prior to start, they will complete their first set of surveys.

Table 2: STELLA-FTD Care Partner Activities

Activity	Description	Due
Consent	Care Partner and care recipient consent	Prior to any study activities
Randomized to groups	Either test or control group	After consent completed
Assessments	Baseline Assessment	4 weeks prior to STELLA-FTD start

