Care Partners may fill out weekly "Orbit" surveys that were developed by the Oregon Roybal Center for CAre Support Translational Research Advantaged by Integrating Technology (ORCASTRAIT), housed at the Oregon Alzheimer's Disease Research Center. The survey includes the "ORCASTRAIT Care Partner Weekly Survey," which measures Care Partner emotional and physical strain, The 4-item ZBI, a brief measure of burden ($\alpha=.78$),³¹ medication use, likelihood of placing their care recipient into long term care (e.g., assisted living, memory care), and frequency of contact with both their and their family member with dementia's clinical providers. Also included in the Orbit survey is the "ORCASTRAIT Caregiver Cost Survey," which measures out-of-pocket costs. The two surveys will take approximately 1-15 minutes (total) to fill out and will be emailed to the Care Partners weekly using REDCap or Qualtrics. Each group (test and control) will receive Orbit surveys specific to their group.

We will use focus groups to seek feedback on the handbooks and *The FTD Roadmap*©. While these materials were developed with pilot feedback, input from a larger sample will provide information on further refinement of the materials to be used in future studies.

Care Partners who are unable to complete all STELLA-FTD components will remain in the study and we may collect the data noted in Table 3. Care Partners who do not complete any trainings, or are unwilling or unable to adequately follow study instructions and participate in study procedures, may be withdrawn from the study. We will retain and analyze any data from their participation. They may also be asked to complete the surveys, despite not completing all of the trainings.

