H1: Upon completion of the STELLA-FTD 8-week intervention, care partners in the test group will have significantly lower (better) burden scores than those in the control group. For H1, we will employ a mixed effects model to analyze whether the change in reactivity on the RMBPC (2) differs across groups (test vs. control) over the intervention period. Two fixed effects will be included in the model: 1) Group effect will be included as a dichotomous categorical variable (test vs. control); 2) Time effect will be included as a continuous variable. The interaction between group and time (group x time) will also be included. Random intercepts will be incorporated for subject specificity in the model to account for clustering effect within subject over time. We will perform a hypothesis test for the coefficient of the interaction term (group x time) to assess the difference in change on primary outcome in the intervention group as compared to control group, over time. We will extend the model to include diagnosis type (e.g., PPA, bv-FTD), frequency of behavioral symptoms as measured on the RMBPC (2), socio-demographic covariates (e.g. sex, age, sex, education) and external support group use. Results will be considered significant at $\alpha = 0.05$, with two-sided test. Similar analyses will occur at Week 20 and 36.

Aim 2. Test the mechanism of action of STELLA-FTD by isolating the ABC training component (the behavior change technique) and determining its relationship to self-efficacy (the intervention target) and burden (the primary outcome) (Figure A).

The statistical analyses for Aim 2 will be carried out in three steps to investigate the mediated effect of self-efficacy ⁽³⁾ on the association between intervention and primary outcome, the RMBPC ⁽²⁾ reactivity score.

H2: Care partners who receive STELLA-FTD with ABC training (the test group) will have significantly higher self-efficacy scores ⁽³⁾ than the control group. To test H2 in the first step, we will employ a similar mixed effect model as H1. The mixed effect model analyses will be performed on total self-efficacy score as the outcome. A hypothesis test for the coefficient of the interaction term (group x time) will be performed to assess the difference in change on self-efficacy score in the test group as compared to control group, over time.

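### Care partners may be withdrawn for poor adherence after randomisation, and outcome surveys from non-completers are optional, so their post-intervention scores may be lost

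*Combined protocol and SAP*

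**What the plan says.** All references are to the combined protocol and SAP.

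- **Section 6, Anticipated challenges**, among its scheduling concessions: "Care Partners can skip up to 3 sessions and still remain in the study".
- **Section 6, Measures**: care partners who cannot complete every component stay in the study, and the team *may* collect the Table 3 data from them. Withdrawal is permitted, at unspecified discretion, for "Care Partners who do not complete any trainings, or are unwilling or unable to adequately follow study instructions" and take part in procedures. Data already obtained are kept and analysed. The paragraph ends: "They may also be asked to complete the surveys, despite not completing all of the trainings".
- **Table 3** contains the primary outcome (RMBPC) and the mediator (self-efficacy), so the optional wording covers both.
- **Table 2** places randomisation after consent and ahead of the baseline assessment and all sessions.
- **Section 6, text before Table 3**: people who drop out are asked for an Exit Survey.
- **Section 6, text after Table 3**: surveys are sent electronically with automatic reminders and a possible call. Whether this continues after withdrawal is not said.
- **Section 8** specifies a random-intercept mixed model for H1 and a similar one for H2. It gives no analysis population, no intention-to-treat statement, no missing-data method and no sensitivity analysis.

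**The concern.** A withdrawal made after randomisation because of poor adherence is a selection on behaviour that the assigned arm can influence. The test arm is told to write, share, test and revise ABC plans, so failing to follow instructions covers more ground there than in the control arm. Only care partners are described as blinded, and each arm has its own guides. A discretionary judgement by someone who knows the arm is therefore possible.

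Keeping scores already collected does not supply the scores due after the intervention and at weeks 20 and 36 if the team chooses not to ask for them. A mixed model handles such gaps without bias only if, given the observed data, missingness is unrelated to the unseen scores. Loss driven by poor adherence puts that in doubt. Lower reactivity is better, so if the people lost do worse and more are lost from the test arm, ABC training looks better than it is among those randomised.

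**Working it through.** **1. The plan's own figure.** Section 4 takes a standardised effect of 0.3, 80% power, two-sided alpha 0.05 (two-sidedness is stated for H1 in section 8), and "three repeated measurements and an Intra-Class Correlation (ICC) =0.5 to 0.6 in compound symmetry covariance structure". With m = 3:

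n per group = 2(1.96 + 0.842)² × [1 + (m − 1) × ICC] / (m × 0.3²)

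- ICC 0.5: 116.3, so 117.
- ICC 0.6: 127.9, so 128.

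Both match the plan. Inflating 2 × 128 = 256 for 15% attrition gives 256 / 0.85 = 301.2, so 302, against 300 planned. The sample size is not in error.

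**2. Room for further loss.** The 15% allowance lists schedule demands, illness and death. Withdrawal by the team is not among them. Assume 1:1 allocation (the ratio is not stated), so 150 per arm, and

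power = Φ(0.3 / √{2[1 + 2 × ICC] / (3n)} − 1.96):

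| Loss | n per arm | Power, ICC 0.5 | Power, ICC 0.6 |
|---|---|---|---|
| 15% | 127.5 | 83.5% | 79.9% |
| 20% | 120 | 81.2% | 77.4% |
| 25% | 112.5 | 78.7% | 74.8% |

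At ICC 0.6 there is no slack beyond the planned 15%.

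**3. Bias in a complete-case comparison.** Let a proportion q of an arm be lost, with outcomes g SD worse than those retained. The retained mean then looks better than the full-arm mean by q × g, so the group difference shifts by (q_test − q_control) × g. The documents give none of these inputs, so all are assumptions.

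- 15% v 5%, g = 0.3 to 0.8: 0.10 × 0.3 = 0.03 to 0.10 × 0.8 = 0.08 SD, or 10% to 27% of 0.30.
- A 5-point difference, same g: 0.015 to 0.04 SD, or 5% to 13%.
- Equal loss and equal g: zero.

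**4. Bias in the planned model.** The planned analysis is not complete-case. The random-intercept model with group, time and group × time keeps the earlier scores of people who are lost. It was simulated with 150 per arm, ICC 0.55, visits at weeks 1, 4, 8 and 12, 15% v 5% loss and g = 0.3 to 0.8. The table gives the shift in the 8-week group difference against the same model with no loss:

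| When the gap appears | Shift (SD) | Share of 0.30 |
|---|---|---|
| After week 4; last score at week 4 | 0.023 to 0.061 | 8% to 20% |
| After week 4; last score at week 8 | 0.017 to 0.045 | 6% to 15% |
| Half already present at baseline | 0.009 to 0.044 | 3% to 15% |
| All present from baseline | 0.004 to 0.019 | 1% to 6% |

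The expected generalised-least-squares estimate, with the gap growing linearly after week 4, agrees to within about 0.003 SD. The smallest value varies between 0.004 and 0.006 SD across simulation runs, so a fair summary is about 0.01 to 0.06 SD, or about 2% to 20% of the target.

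**5. The two statements on staying in the study.** Anticipated challenges ties remaining to no more than 3 skipped sessions, which implies a limit without stating what happens beyond it. Measures says people who cannot complete all components remain, with no limit. A care partner who attends four of the eight sessions is kept under one and, by implication, not under the other.

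**The case against.** A reader might infer that anyone who misses sessions is removed, that their later scores are never requested, and that the trial therefore loses its non-adherent participants. The documents do not support this. Partial completers are expressly kept. The named grounds for withdrawal are completing no training or not adequately following instructions and procedures. A limit beyond 3 skipped sessions is only implied, in a list of concessions. Withdrawal is optional, data in hand are analysed, and later surveys may still be requested. The general reminder process is not made conditional on attendance.

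On size, the complete-case 10% to 27% does not describe the planned model, which recovers part of the loss from earlier scores, most of all when non-adherent people already differ at baseline. The assumed 15% loss to withdrawal in the test arm alone equals the plan's whole all-cause allowance, so it is a demanding scenario. Both arms receive the same basic curriculum, and no arm-specific loss is reported.

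All of this stands, and it limits the certainty and size of the claim. It does not remove the gap: nothing in the plan obliges the team to request the primary outcome from a non-adherent care partner, and no analysis rule covers its absence.

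**Conclusion.** The concern holds as a permitted loss, not a certain one. As written, the plan allows adherence-based withdrawal after randomisation and leaves outcome collection from those withdrawn, and from partial completers, to discretion. Following it faithfully could leave post-intervention RMBPC and self-efficacy scores missing selectively.

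The 2% to 20% range rests on assumed arm-specific loss, an assumed outcome gap, 1:1 allocation and ICC 0.55. The direction favours ABC only if loss is higher in the test arm and those lost do worse; it reverses if either condition is reversed. The documents do not allow an actual bias to be calculated. The case for acting is that scores not requested at the time cannot be recovered later. The two statements about remaining in the study are inconsistent and must be reconciled.

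**What to change.** Keep whatever discretion is wanted over session attendance, but separate it from outcome collection. In section 6 (Measures), change *may* to *will* along these lines:

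> *Every randomised care partner will be sent every scheduled RMBPC and self-efficacy survey through week 36, with the usual reminders, whatever their session attendance, unless they withdraw consent to follow-up or are excused because the care recipient has died.*

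The last exception follows section 5(b), which already excuses care partners in that event.

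In section 8, add:

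- H1 and H2 include all randomised care partners in the group to which they were assigned.
- A missing-not-at-random sensitivity analysis varies the assumed outcome of those with missing post-intervention scores, by arm, over a stated range such as 0 to 0.8 SD worse.
- Withdrawals are reported by arm, with the reason and whether the team or the participant initiated them.

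Reconcile Anticipated challenges with Measures, so that any attendance limit is stated once and applies to sessions, not to outcome surveys.

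The cost is a wording amendment and some extra reminders and calls to people who have stopped attending. The surveys are already electronic with automatic reminders, so this is a cheap improvement.
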